### **Proportion of Patients Who Lose <15 Letters in BCVA score from Baseline**

For proportion of patients who lose <15 letters in BCVA score from baseline to the average over Month 9 and Month 10, the proportion of patients in each treatment group and the overall difference in proportions between treatment groups will be estimated using the weighted average of the observed proportions and the differences in observed proportions over the strata defined by randomization factors using the Cochran-Mantel-Haenszel weights ([Cochran 1954](#); [Mantel and Haenszel 1959](#)). Confidence intervals of the proportion of patients in each treatment group and the

overall difference in proportions between treatment groups will be calculated using the normal approximation to the weighted proportions (Mehrotra and Railkar 2000). Data for patients who receive rescue treatment or undergo explantation prior to Month 9 will be censored for binary endpoints. For all other patients, the analysis will be based on the available data at each visit, with no imputation for missing data.

In addition, figures for proportion of patients who lose <15 letters in BCVA score from baseline over time will be provided.

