### **5.1.1.2 Rescue Treatment with Open-Label Ranibizumab For Implant Patients**

Rescue treatment with open-label ranibizumab (0.5-mg ITV injections of 10-mg/mL formulation) for patients in the Implant arm is allowed only under the following circumstances:

- Approximately 1 month and/or 2 months after occurrence of vitreous hemorrhage, if vitreous hemorrhage causes loss in BCVA, and neither assessment of the macula nor SD-OCT can be performed successfully (see Section [5.1.1.4](#))
- At the time a patient meets criteria for lack of clinical efficacy (see Section [5.1.1.3](#))
- In the case of progressive worsening of BCVA and/or CFT due to wet AMD activity across two consecutive scheduled visits, only if the patient does not meet refill criteria. If a treatment is clinically necessary due to the progressive clinical worsening per the investigator's judgment, rescue treatment must be discussed and agreed upon by the Medical Monitor prior to being introduced.

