**Rescue Criteria:** Rescue treatment with open-label ranibizumab (0.5 mg intravitreal injections of 10 mg/mL formulation) for patients in the Implant arm is allowed only under the following circumstances:

- Approximately 1 month and/or 2 months after occurrence of vitreous hemorrhage, if vitreous hemorrhage causes loss in BCVA, and neither assessment of the macula nor SD-OCT can be performed successfully.
- At the time a patient meets criteria for LCE (see below).
- In the case of progressive worsening of BCVA and/or CFT due to wet AMD activity across two consecutive scheduled visits, only if the patient does not meet refill criteria. If a treatment is clinically necessary due to the progressive clinical worsening per the investigator's judgment, rescue treatment must be discussed and agreed upon by the Medical Monitor prior to being introduced.

**Lack of Clinical Efficacy Criteria:** If a study patient randomized to the Implant treatment arm meeting criteria for LCE, he or she will receive a rescue injection with open-label ranibizumab at the time of meeting LCE. In addition, he or she will receive a mandatory refill at the 100 mg/mL formulation one month after the rescue intravitreal injection. After that, the 100 mg/mL formulation will be used for all future refills, whenever the patient meets refill criteria. The LCE criteria are as follows:

- Loss in BCVA of  $\geq 15$  letters from the best recorded BCVA on study following two consecutive ranibizumab Implant refills (as per protocol-specified refill criteria)

occurring 1 month apart due to nAMD disease activity and not attributable to a change in the ocular media (i.e., cornea, lens, aqueous or vitreous humor, epiretinal membrane development, etc.) unless there is at least a five-letter increase in BCVA, in which case a refill will occur.

and/or

- Increase in CFT  $\geq 150$   $\mu\text{m}$  from the lowest CFT measurement on study following two consecutive ranibizumab Implant refills (as per protocol-specified refill criteria) occurring 1 month apart due to nAMD disease activity and not attributable to a change in the ocular media (i.e., cornea, lens, aqueous or vitreous humor, epiretinal membrane development, etc.) unless there is a decrease in CFT  $\geq 75$  microns from the last refill, in which case a refill will occur.

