An additional MMRM analysis will be performed including all observed measurements. That is, all observed BCVA data will be included regardless of whether patients received rescue treatment or discontinued study treatment due to AE or LCE. Best corrected visual acuity (BCVA) assessments at the time of explant will be censored. This analysis evaluates the treatment policy of PDS with rescue therapy versus the monthly intravitreal ranibizumab.

From the recent end of Phase II meeting with the US FDA on 23 March 2018, the Agency agreed that the change in BCVA from baseline averaged over Month 9 and Month 10 is an appropriate primary endpoint for the Phase III study to assess the non-inferiority (NI) in visual acuity between the Implant and intravitreal arms with an NI margin of 4.5 letters. This NI margin will be used as a reference to assist data interpretation in this preliminary assessment.

To support the interpretation of BCVA change from baseline over time, figures for the adjusted mean change from baseline over time through Month 10 will be provided.

- Trimmed mean analysis for change in BCVA score from baseline averaged over Month 9 and Month 10:

A trimmed mean analysis ([Permutt and Li 2016](#)) will be performed using an analysis of covariance (ANCOVA model) for adjustment for covariates. The dependent variable in the ANCOVA model is the average of Month 9 and Month 10

assessments in change from baseline in BCVA score (if one of the two assessments is missing, the non-missing assessment will be used), and the independent variables are the treatment group, baseline BCVA score (continuous), and the randomization stratification factor of baseline ( $\leq 65$  letters vs.  $\geq 66$  letters) and number of anti-VEGF-intravitreal injections ( $\leq 3$  vs.  $\geq 4$ ).

Patients will be considered to have the worst outcomes and will be trimmed from analysis if any of the following occurs:

- Patients in the PDS arm receive a rescue treatment (intravitreal injection) or undergo explantation prior to Month 9
- Patients in all treatment arms discontinue study treatment due to LCE or AE prior to Month 9
- Patients in all treatment arms have a missing Month 9 assessment and discontinue study treatment due to LCE or AE at Month 9
- Patients in all treatment arms have missing Month 9 and Month 10 assessments and discontinue study treatment due to LCE or AE at Month 10

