#### **Additional Efficacy Analyses Focused on BCVA Parameters**

- The mean average change from baseline through Month 9 (AUC-like endpoint) in BCVA and 95% CIs will be generated for each treatment arm.
- Summary statistics and figures by treatment arm showing the proportion of patients losing <15 letters, <10 letters, <5 letters, and <0 letters over time through Month 10 will be provided.
- Change from baseline in BCVA over time through Month 10 measured under low luminance conditions will be summarized by treatment arm using descriptive statistics.

Data for patients who receive rescue treatment or undergo explantation prior to Month 9 will be censored. Missing data will not be imputed.

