#### **4.4.2.4 Other Exploratory Efficacy Endpoints**

Other exploratory efficacy endpoints listed in Section 2.2.5 will be summarized using descriptive statistics. Observed data will be used.

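### The between-arm proportion losing fewer than 15 letters leaves out rescued or explanted patients, who can come only from the PDS arms, and has no all-observed counterpart

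*SAP*

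**What the plan says.** The letter-loss part of SAP Section 4.4.2.1 gives a difference in proportions weighted by Cochran-Mantel-Haenszel weights over the randomization strata, with a normal-approximation confidence interval. Two sentences settle who is counted: "Data for patients who receive rescue treatment or undergo explantation prior to Month 9 will be censored for binary endpoints", and "For all other patients, the analysis will be based on the available data at each visit, with no imputation for missing data".

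The by-arm summaries of patients losing fewer than 15, 10, 5 and 0 letters, listed next in the same section, follow the same rule: "Data for patients who receive rescue treatment or undergo explantation prior to Month 9 will be censored. Missing data will not be imputed".

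Protocol Section 5.1.1.2 confines rescue: open-label ranibizumab "for patients in the Implant arm is allowed only under the following circumstances". These are vitreous hemorrhage with BCVA loss when neither the macula nor the OCT can be assessed, meeting the lack-of-clinical-efficacy criteria, and, as SAP Section 2 repeats, "In the case of progressive worsening of BCVA and/or CFT due to wet AMD activity across two consecutive scheduled visits". SAP Section 4.1.1 analyses anyone who received an Implant as a PDS patient.

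For mean BCVA change, Section 4.4.2.1 adds a second repeated-measures model that keeps BCVA measured after rescue. No such version is specified for the proportion.

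**The concern.** The rescue or explant comes before Month 9 and the endpoint is the Month 9/10 average. A censored patient therefore has no usable value and leaves both numerator and denominator. The SAP does not define censoring for a binary endpoint, but with no imputation the result is the same on any reading.

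The removal is one-sided by construction. An intravitreal-arm patient cannot be rescued or explanted. One who stops treatment is asked to keep attending monthly visits (Protocol Section 4.7.2) and stays in on available data.

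The removal is also partly related to outcome, because the triggers include falling BCVA and lack of clinical efficacy. The link is not exact: the efficacy criterion measures loss from the best on-study BCVA rather than from baseline, and rescue can follow a change in CFT alone.

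What is at stake is how the PDS arms appear beside monthly injections on keeping vision, in an estimate that the SAP offers as a preliminary assessment of visual acuity.

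**Working it through.** **Plan's own figure.** The SAP gives no figure for this proportion. Its only precision figure for PDS against intravitreal is an 80% interval extending 2.62 letters for BCVA change, with SD 10. With 60 and 40 patients: 1.2816 × 10 × √(1/60 + 1/40) = 2.616. This reproduces the figure and confirms that the plan works with 60 against 40.

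**Inputs.** Arm sizes of 60 and 40 come from the documents. Three quantities are assumptions, because the documents give none of them:
- f, the share of a PDS arm rescued or explanted before Month 9;
- p_kept, the proportion of the remaining PDS patients losing fewer than 15 letters, set at 0.95;
- p_removed, the same proportion among removed patients, taken from 0 to 1.

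**Formula.** The censored estimate is p_kept. The all-observed estimate is (1 − f) × p_kept + f × p_removed. The bias (censored minus all observed) is f × (p_kept − p_removed); positive values favour PDS. The intravitreal arm has f = 0, so the whole bias carries into the difference.

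Bias in percentage points, p_kept = 0.95:

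| f | p_removed = 1 | 0.95 | 0.75 | 0.50 | 0 |
|---|---|---|---|---|---|
| 5% | -0.25 | 0 | 1.0 | 2.25 | 4.75 |
| 10% | -0.5 | 0 | 2.0 | 4.5 | 9.5 |
| 20% | -1.0 | 0 | 4.0 | 9.0 | 19.0 |

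**Comparison with precision.** The unstratified 95% half-width, with 95% in both arms, is 1.96 × √(0.95 × 0.05 × (1/60 + 1/40)) = 0.0872, or 8.7 points. With 54 against 40 it is 8.9 points. At f = 10%, the bias exceeds 8.7 points only if p_removed is below 0.95 − 0.0872/0.10 = 0.078. It reaches half of the half-width at 0.95 − 0.0436/0.10 = 0.514.

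**Whole-number example.** Take 60 PDS patients, 6 of them removed, and 3 of the 54 kept patients losing 15 letters or more. Intravitreal: 38/40 = 95.0%.
- Censored: 51/54 = 94.4%, difference -0.6 points.
- All observed, 3 of the 6 removed losing 15 or more: 54/60 = 90.0%, difference -5.0.
- All observed, none of the 6 losing 15 or more: 57/60 = 95.0%, difference 0.

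The censored result is the same in the last two cases, so it cannot tell a reader which applies.

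**The case against.** **It is supportive only.** SAP Section 4.4 restricts testing to the primary endpoint, and Section 4.4.2 says the study is not powered for these comparisons. This stands. Time to first refill and type I error are untouched.

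**Other output may reveal the problem.** The proportion losing 15 letters or more is the complement of this endpoint and is listed in SAP Section 2.2.5. Section 4.4.2 promises descriptive summaries of all exploratory endpoints, and Section 4.4.2.4 adds: "Other exploratory efficacy endpoints listed in Section 2.2.5 will be summarized using descriptive statistics. Observed data will be used". A by-arm observed-data summary may therefore exist, and the proportions meeting the efficacy-failure criteria or requiring explantation are also listed. This stands in part: none of these is a specified between-arm difference with an interval, and not every rescue route is covered.

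**A reader might infer that the section contradicts itself.** In the trimmed mean, "Patients will be considered to have the worst outcomes and will be trimmed from analysis if any of the following occurs", and the first listed event is "Patients in the PDS arm receive a rescue treatment (intravitreal injection) or undergo explantation prior to Month 9". The documents do not support a contradiction. Censoring after rescue or explant is the usual rule in this SAP (the main repeated-measures model, the ANCOVA, CFT, MacTSQ). The trimmed mean is a different estimand, and it also takes these patients out of the mean.

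**A reader might also infer that rescued or explanted patients should simply be counted as vision failures.** That does not match the trimmed mean. Three of its four criteria cover discontinuation of study treatment for lack of efficacy or an adverse event in all arms, and equal fractions are trimmed from both arms. A composite built on rescue and explant alone could penalise only PDS. If, say, 5% of intravitreal patients stopped for an adverse event, the full criteria would lower that arm from 95% to 0.95 × 0.95 = 90.25%, a 4.75-point shift that the narrower composite omits. It would also label non-visual events as vision loss: rescue for CFT alone, or explant for Implant damage or pregnancy (Protocol Table 6).

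**Conclusion.** The concern holds in a limited form. The only specified between-arm letter-loss difference omits a partly outcome-related group that can arise only in the PDS arms, and no all-observed version accompanies it.

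The likely direction favours PDS because several triggers are visual, but the documents do not establish it. The sign turns slightly the other way if all removed patients kept vision. At an assumed 10% removed, the bias runs from -0.5 to 9.5 points and is 4.5 points if half of those removed kept vision. It would usually sit inside the confidence half-width while still being large enough to change how the estimate reads. The sizes rest on assumed rates and an unstratified calculation.

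**What to change.** In the letter-loss part of SAP Section 4.4.2.1:
- Add the same weighted difference and confidence interval using all observed Month 9 and Month 10 BCVA, regardless of rescue or explant, and show it beside the censored version.
- Apply the all-observed version to the by-arm summaries at 15, 10, 5 and 0 letters as well.
- Report the number and percentage censored in each arm, by reason.
- If a composite is also wanted, define failure with all of the trimmed-mean criteria, including discontinuation for lack of efficacy or an adverse event in every arm. Label it treatment failure or loss of 15 letters or more, not vision loss.

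The cost is SAP wording and a rerun on data already scheduled for collection: Implant patients who stop treatment keep attending monthly visits until the last patient's Month 9 visit (Protocol Section 4.6.10.3).

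There are three downsides. PDS may look less favourable. The all-observed version includes vision held on rescue injections or on post-explant intravitreal ranibizumab, which is the control drug (Protocol Section 4.7.2), so it can flatter PDS or draw the arms together; this is why both versions are needed. Some values will still be missing: patients who leave the study at explant have no further monthly visits (Protocol Section 4.6.10.4), and explanted patients enrolled last may have no Month 10 visit.

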#### **Additional Efficacy Analyses Focused on BCVA Parameters**

- The mean average change from baseline through Month 9 (AUC-like endpoint) in BCVA and 95% CIs will be generated for each treatment arm.
- Summary statistics and figures by treatment arm showing the proportion of patients losing <15 letters, <10 letters, <5 letters, and <0 letters over time through Month 10 will be provided.
- Change from baseline in BCVA over time through Month 10 measured under low luminance conditions will be summarized by treatment arm using descriptive statistics.

Data for patients who receive rescue treatment or undergo explantation prior to Month 9 will be censored. Missing data will not be imputed.

#### **4.4.2.2 Anatomical Outcomes**

The change in CFT (with and without inclusion of pigment epithelium thickness and its elevation in the foveal center, as assessed by the Reading Center) from baseline at Month 9 will be compared between each PDS arm and the intravitreal arm using the same analysis method (MMRM) and data handling rules that are used for the change from baseline in BCVA score at the average of Month 9 and Month 10. Comparisons between the Implant arms and the intravitreal arm will be made using a contrast at Month 9. Figures for adjusted mean change from baseline in CFT over time through Month 9 will be provided. Descriptive summaries for change from baseline in CFT through Month 9 will also be provided. Data for patients who receive rescue treatment or undergo explantation prior to Month 9 will be censored.

In addition, a descriptive summary for change from baseline in CFT over time through the end of the study will be provided. This summary will include all observed data without censoring observations after use of rescue treatment or after explant.

Changes from screening in total lesion area, area of CNV lesion, and CNV leakage over time through Month 9, as assessed by fluorescein angiography, as well as changes in CNV perfusion over time through Month 9, as assessed by OCT angiography will be summarized using descriptive statistics. Data for patients who receive rescue treatment or undergo explantation prior to Month 9 will be censored. Missing data will not be imputed.

#### **4.4.2.3 Patient-Reported Outcomes (MacTSQ)**

The MacTSQ was developed to provide a means of evaluating satisfaction with therapies for macular disease. The MacTSQ provides two subscale scores: impact of treatment and information provision and convenience. Higher scores for the total scale and the subscales represent increased satisfaction with treatment.

The MacTSQ score including both total score and subscale scores at scheduled visits will be summarized using descriptive statistics based on the observed data. Data will be specifically imputed using the rules as follows:

- Subscale 1 (information provision and convenience): Set the subscale 1 value to missing if any of the items in the subscale is missing.
- Subscale 2 (impact of treatment score): Set the subscale 2 value to missing if two or more items in the subscale 2 are missing. If only one item is missing, impute the item value based on the average of the other five items.
- Single scale (overall score): Set the single scale value to missing if four or more items are missing. If three or less items are missing, impute the missing item values based on the average of the other available items.

Data for patients who receive rescue treatment or undergo explantation prior to Month 9 will be censored.

#### **4.4.2.4 Other Exploratory Efficacy Endpoints**

Other exploratory efficacy endpoints listed in Section 2.2.5 will be summarized using descriptive statistics. Observed data will be used.

### **4.5 PHARMACOKINETIC AND PHARMACODYNAMIC ANALYSES**

Analyses were performed using a PK-PD model, and this model was used to run clinical trial simulations to inform Phase III clinical study design (RPDS EOP2 PMP, February 2018).

Individual and mean serum ranibizumab concentrations over time will be tabulated and plotted by refill number. The serum PK of ranibizumab will be characterized by estimating the AUC,  $C_{max}$ ,  $t_{max}$ ,  $t_{1/2}$ , and  $C_{trough}$  between dose intervals. Estimates for these parameters will be tabulated and summarized by descriptive statistics. Additional PK analyses may be conducted as appropriate.

### **4.6 SAFETY ANALYSES**

The safety analyses will use the safety population as described in Section 4.1 and 4.1.2. Missing data will not be imputed.

Adverse events (AEs) are coded using the current MedDRA version. Rates will be provided for intravitreal patients and PDS patients by dose arm and pooled across PDS arms.

For safety analyses, unless otherwise specified, AEs after the start of study treatment (intravitreal injection or Implant) will be included in the analyses; AEs from patients who are explanted will be included up to a follow-up period of 90 days after explant; the post-explant ocular AEs considered related to PDS will also be included in the analyses regardless of the timing of the AE onset. To fully characterize these patients' safety, a listing will be provided for ocular AEs that occurred  $\geq 90$  days after explant.

Frequency tables including patient incidence rates will be provided for the following:

- Ocular AEs and SAEs (study and fellow eye)
- Non-ocular AEs and SAEs (study and fellow eye)
- Adverse events of special interest (study and fellow eye)
  - AEs resulting from medication errors
  - An AE considered to be sight threatening
  - Suspected transmission of an infectious agent by the study drug
  - AEs resulting from use error or from intentional misuse of the PDS
  - ADEs, that is, AEs that are considered to be related to the PDS and to the use of the PDS
- Adverse events potentially related to the PDS Implant or Implant procedures:
  - Vitreous hemorrhage
  - Endophthalmitis
  - Retinal detachment
  - Conjunctival retraction
  - Conjunctival erosion
  - Conjunctival bleb
  - Conjunctival filtering bleb leak
  - Hyphema
  - Cataract

For AEs potentially related to the PDS Implant or Implant procedures in the study eye, incidence tables will be generated using the following time windows relative to first dose or implant surgery:

- $\leq 1$  month (up to the end of Month 1 visit window, 37 days)
- $> 1$  month
- during the entire study

In addition, ocular AEs and SAEs will be provided by causality as determined by the investigator.

Adverse events (AEs) potentially related to the PDS Implant or Implant procedures will be summarized separately for two subgroups of patients based on the IFU version in use at the time of their randomization (before IFU 10 vs. IFU 10 forward). There was a study pause to evaluate post-implantation vitreous hemorrhage and modifications were made beginning with Version 10 with the aim to reduce the risk of vitreous hemorrhages.

Non-ocular AEs and SAEs will be tabulated using the following time windows relative to first ranibizumab injection or device implant following randomization:

- Cumulative rates through 10-month follow-up for each patient
- Cumulative rates for through the end of the study (expected Month 38)

A listing of patients who died during the study will be provided.

The number and percentage of patients with positive serum anti-drug antibodies (ADA) at baseline and post-baseline during the study period will be tabulated. Impact of positive serum ADA on efficacy and safety will be explored. A listing of patients with positive serum antibodies to ranibizumab will be provided.

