The ITV treatment arm patients who are discontinued from study treatment prematurely will be asked to undergo the scheduled monthly assessments until Last Patient In (LPI) Month 9 visit, after which they will be scheduled 30 (+7) days later for their final study visit. The patients who are discontinuing study treatment from the Implant treatment arms will be scheduled, within 7 days after the treatment discontinuation decision is made, for Implant explantation followed by safety visits 1 and 7 ( $\pm 2$ ) days post-explantation. Afterwards, they will be followed in the study, attending their monthly scheduled visits, until LPI Month 9 visit, after which they will be scheduled for the early termination visit (see [Appendix 1](#)). As per investigator judgement, these patients may start an approved anti-VEGF for their AMD once the need for Implant explantation is confirmed and, preferably, after explantation is completed. All explanted Implants with their remaining content will be returned to the designee of the Sponsor for storage and potential future exploratory analysis (see Section 4.4). A vitreous or aqueous humor sample will be collected at the start of explantation for patients undergoing an explantation procedure (see [Appendix 19](#)).

Patients who withdraw from the study prior to scheduled study completion will be asked to return for an early termination evaluation 30 (+7) days following their last study treatment for monitoring of adverse events and early termination visit assessments if they are in the ITV treatment arm. The patients who are discontinuing the study from the Implant treatment arms will be scheduled for Implant explantation within 7 days of the treatment discontinuation decision, followed by Safety Visits 1, 7 ( $\pm 2$ ), 30 ( $\pm 7$ ), and 60 ( $\pm 7$ ) days post-explantation after which they will be scheduled for the early termination visit 30 (+7) days later. As per investigator judgment, these patients may start an approved anti-VEGF treatment for their AMD once the need for Implant explantation is confirmed and, preferably, after explantation is completed. All explanted Implants with remaining content will be returned to the designee of the Sponsor for storage and potential future exploratory analysis (see Section 4.4). A vitreous or aqueous humor sample will be collected at the start of explantation for patients undergoing an explantation procedure (see Appendix 19).

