##### **5.4.2.2 Events That Occur After Study Drug Initiation**

After initiation of study drug, serious adverse events, and any AESI will be reported until 30 (+7) days after the last study drug administration for the ITV injection treatment arm and until 90 (+7) days after the Implant explantation for the Implant treatment arms. However, if any patient continues to be followed in the study after an early discontinuation of the treatment, the adverse events will be reported until their study completion. Investigators should record all case details that can be gathered immediately (i.e., within 24 hours after learning of the event) on the adverse event eCRF and submit the report via the electronic data capture (EDC) system. A report will be generated and sent to Roche Safety Risk Management by the EDC system.

In the event that the EDC system is unavailable, the Serious Adverse Event/Adverse Event of Special Interest Reporting Form provided to investigators should be completed and submitted to the Sponsor or its designee immediately (i.e., no more than 24 hours after learning of the event), either by faxing or by scanning and emailing the form using the fax number or email address provided to investigators. Once the EDC system is available, all information will need to be entered and submitted via the EDC system.

Instructions for reporting post-study adverse events are provided in Section 5.6.

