## **5.6 POST-STUDY ADVERSE EVENTS**

The Sponsor should be notified if the investigator becomes aware of any serious adverse event that occurs after the end of the adverse event reporting period (defined as 30 (+7) days after the last dose of study drug for ITV treatment arm and 90 (+7) days after the Implant explantation for patients in the Implant treatment arms), if the event is believed to be related to prior study drug treatment or due to the Implant.

These events should be reported through use of the Adverse Event eCRF. However, if the EDC system is not available, the investigator should report these events directly to the Sponsor or its designee, either by faxing or by scanning and emailing the Serious Adverse Event/Adverse Event of Special Interest Reporting Form using the fax number or email address provided to investigators.

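### SAP 4.6 stops counting most adverse events 90 days after explant but sets no matching limit for intravitreal patients who stop treatment, so late non-ocular events have no assured place in any table or listing

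*SAP*

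**What the plan says.** SAP 4.6 opens with a general rule for both routes of treatment: "For safety analyses, unless otherwise specified, AEs after the start of study treatment (intravitreal injection or Implant) will be included in the analyses". It then restricts one group: "AEs from patients who are explanted will be included up to a follow-up period of 90 days after explant". There is one exception: "the post-explant ocular AEs considered related to PDS will also be included in the analyses regardless of the timing of the AE onset". For late events, "a listing will be provided for ocular AEs that occurred" 90 or more days after explant. Nothing equivalent is provided for non-ocular events, apart from the listing of patients who died.

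The same section also sets reporting windows. AEs potentially related to the Implant or its procedures are tabulated up to 1 month, beyond 1 month and over the whole study. Non-ocular AEs and serious AEs (SAEs) are tabulated through 10 months and then as "Cumulative rates for through the end of the study (expected Month 38"). None of these windows mentions explant.

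The protocol keeps early treatment discontinuers in follow-up. In section 3.1, "The ITV treatment arm patients who are discontinued from study treatment prematurely will be asked to undergo the scheduled monthly assessments" until the last patient's Month 9 visit. Explanted patients who stay in the study attend monthly visits to the same point. Section 5.4.2.2 says that for patients followed after stopping treatment early, "the adverse events will be reported until their study completion". The standard reporting period, in sections 5.4.2.2 and 5.6, is 30 (+7) days after the last dose in the intravitreal arm and "90 (+7) days after the Implant explantation for patients in the Implant treatment arms". The treatment-emergent definition in Protocol 6.5.1 has no 90-day limit. The SAP introduces that limit, and it states that it supersedes the protocol's analysis plan.

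**The concern.** The counting rule depends on the arm, while the data collection does not. A patient explanted early who stays in the study supplies AE data for months, and under SAP 4.1.2 stays in the PDS denominator, but most events after day 90 do not enter the numerator. An intravitreal patient who stops injections and stays in the study has no such limit.

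Three things are at stake. A non-fatal non-ocular SAE, such as an arterial thromboembolic event (a potential risk named in Protocol 5.1), could be collected and then shown nowhere in the AE outputs. For late ocular events, tabulation in the PDS arms turns on a relatedness judgement, and Protocol 4.2.1 says site staff are not masked to Implant versus intravitreal treatment. Finally, two programmers could read the section differently and produce different end-of-study SAE tables.

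**Working it through.** The plan states no figure on this point to reproduce. The check sets the counting rule against the collection rule and then sizes the gap.

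**Step 1. The same event under each rule.** Take a patient who stops treatment early, stays in follow-up, and has an event more than 90 days after explant (PDS) or after the last injection (intravitreal).

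| Event | PDS, explanted | Intravitreal, stopped |
|---|---|---|
| Ocular, considered PDS-related | Tabulated and listed | Not applicable |
| Ocular, not considered PDS-related | Listed only | Tabulated |
| Non-ocular, non-fatal | No AE table or listing | Tabulated |
| Fatal | Patient appears in deaths listing | Tabulated, and in deaths listing |

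This is the reading in which the whole-study windows do not lift the 90-day limit. If they do lift it, the non-ocular event is tabulated in both columns. SAP 4.1 separately lists all AEs from sites with GCP non-compliance, so those sites are an exception.

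**Step 2. Uncounted follow-up per affected patient.** Inputs: accrual of about 24 months (Protocol 3.1); follow-up to the last patient's Month 9 visit; limit of 90 days, about 3 months.

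- Time from Day 1 to that visit: 9 months for the last patient, 24 + 9 = 33 months for the first, and (9 + 33)/2 = 21 months on average if accrual is uniform (assumption).
- Uncounted time = time to that visit − month of explant − 3, not below zero.

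| Explant at | Last patient in | Mean | First patient in |
|---|---|---|---|
| Month 1 | 9 − 1 − 3 = 5 | 21 − 1 − 3 = 17 | 33 − 1 − 3 = 29 |
| Month 3 | 3 | 15 | 27 |
| Month 6 | 0 | 12 | 24 |

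Patients who leave the study after explant have their final visit at 90 (+7) days, so at most the 7-day window is lost.

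**Step 3. Illustrative effect on the tables.** The documents give neither an explant rate nor an SAE rate. Assume that 2% to 10% of the 180 PDS patients are explanted at Month 3 and stay in the study, and that non-ocular SAEs occur at 0.05 to 0.20 per patient-year. Mean uncounted time is T = 15/12 = 1.25 years.

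- Follow-up left out: 3.6 to 18 patients × 1.25 years = 4.5 to 22.5 patient-years. Total PDS follow-up to the same visit, ignoring withdrawal, is 180 × 21/12 = 315 patient-years, so the share is 1.4% to 7.1%.
- Patients with an uncounted first non-ocular SAE = 180 × explant proportion × (1 − exp(−rate × T)).
  - Low end: 3.6 × (1 − exp(−0.0625)) = 0.2 patients, or 0.1 percentage points of 180.
  - Middle (5%, 0.10): 9 × (1 − exp(−0.125)) = 1.1 patients, or 0.6 points.
  - High end: 18 × (1 − exp(−0.25)) = 4.0 patients, or 2.2 points.

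The calculation ignores withdrawal and assumes none of these patients already had a counted non-ocular SAE. Both simplifications push the figures up.

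**The case against.** The strongest objection is textual. The general rule carries an explicit reservation for cases specified otherwise, and the section goes on to specify whole-study windows. Read together, these could lift the 90-day limit for the non-ocular table, and then nothing is lost from it. This stands as far as it goes: a reader might infer that late SAEs are certain to vanish, and the text does not support that. It does not settle the matter either, because the windows run from first dose or implant and never say that they override the limit.

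A reader might also infer that the rule pushes PDS event rates below intravitreal rates. The documents do not show this. Among patients who stay in follow-up, the rule removes PDS events only. Among patients who exit, the reporting period is longer in the PDS arms, nominally 90 days after explant against 30 days after the last injection. Without the number of patients in each situation, the net direction is unknown.

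Nor do the documents support the inference that device complications are hidden. A complication that leads to explant occurs before the limit and is counted. Ocular events considered PDS-related count at any time, and other late ocular events are listed. Protocol Table 6 also calls for explant in situations that need not involve any AE, such as observed damage to the Implant.

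Finally, a post-explant limit is defensible in itself. Explanted patients may start another approved anti-VEGF agent, and under Protocol 4.7.2 the sponsor supplies intravitreal ranibizumab until the last patient's Month 9 visit. Counting all later events under PDS mixes treatments. That is a good reason to show an on-treatment table. It does not justify a limit in one group only, or a late listing that omits non-ocular events.

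**Conclusion.** The point holds in a limited form. SAP 4.6 applies an arm-specific counting rule to data collected on the same terms in both groups. On its plain reading, non-fatal non-ocular AEs and SAEs more than 90 days after explant fall outside every AE table and listing, and late ocular events not considered PDS-related are listed but not tabulated. Whether the whole-study windows override this is unclear.

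The effect is confined to patients explanted early who remain in the study. Each loses between 0 and 29 months of counted follow-up for explants at Months 1 to 6. The illustration of 0.2 to 4.0 patients, or 0.1 to 2.2 percentage points of pooled PDS incidence, rests entirely on the assumed explant and SAE rates. It shows scale and is not an estimate. No direction of between-arm bias is established. The 7-day difference between the SAP's 90 days and the protocol's 90 (+7) days is minor.

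The SAP should still be corrected, because a safety plan should leave no collected SAE without a place in the report, and the correction needs no new data.

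**What to change.** In SAP 4.6:

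1. State that the whole-study and end-of-study tables include all AEs collected in every arm, regardless of explant or treatment discontinuation.
2. Give on-treatment tables alongside, using the protocol's own reporting period in each arm: 90 (+7) days after explant for PDS and 30 (+7) days after the last injection for intravitreal patients. Neither set has to be designated the main one.
3. Extend the listing of events 90 or more days after explant to non-ocular AEs and SAEs.

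The cost is a wording change, one extra set of tables and a longer listing. The all-study tables will include some post-explant events that arose under other anti-VEGF treatment, which the on-treatment tables separate out.
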